5 DATA SETS TO BE ANALYSED

Subjects populations:

5.1 Enrolled Population

All recruited patients who provided written informed consent to participate.

5.2 Evaluable Population

Evaluable Population will include all subjects who receive at least one PE treatment with Albutein 5% and also have at least one baseline determination and a measurement of a primary efficacy variable at a subsequent visit: at least one measure of FVC and one measure of ALSFRS-R at baseline visit, and after the baseline visit.

5.3 Per-Protocol (PP) Population

All evaluable subjects who complete the treatment without major protocol deviations which could impact the primary efficacy assessment. The major protocol deviations will be determined in a data review meeting and will be documented in a data review report prior to the database lock.

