6.2.3. Plasma Exchange (PE) Treatments

A maximum of 27 PEs will be conducted over 6 months.

In the first Intensive Treatment Phase, 2 PEs per week will take place for 3 weeks, for a total of 6 PEs. Subsequently, 1 weekly PE for 21 weeks (Maintenance Treatment Phase) will take place to complete the 6 months (24 weeks) of treatment, for a total of 27 PEs.

If there are any important laboratory parameter changes, clinical factors, or AEs that require a PE not to be performed, the actual number of PE sessions may be less than the maximum intended.

PE visits during the Intensive Treatment Phase will be scheduled ± 1 day to the planned day while always maintaining a minimum of 48 hours between two consecutive PEs.

Subsequently, the PE visits during the Maintenance Treatment Phase will be scheduled ± 2 days prior to the planned day.

The subject will remain in the Outpatient Apheresis Unit during the entire PE session and for an appropriate period post PE as determined by the research nurse to ensure that the subject is able to return home in a clinically stable condition.

Before the PE, any abnormal condition observed since the baseline visit or the previous procedure will be recorded as an AE. Concomitant medications that the subject is receiving will also be recorded.

A complete blood count and fibrinogen levels will be determined 10 to 15 minutes before each PE, following the Dartmouth Donor Room policy.

Vital signs (blood pressure, heart rate, body temperature and respiratory rate) and blood oxygen using a pulse oximeter will be measured 10 to 15 minutes before the beginning of each PE, during the PE (30 min after PE procedure starts), and 15 to 30 minutes after the PE procedure. In the case of pertinent abnormalities, the tests will be repeated until normalization or stabilization.

Serum electrolytes (calcium, phosphate, sodium, potassium, chloride, bicarbonate) and coagulation parameters will be measured 15 to 30 minutes after each PE procedure.

Plasma retention sample will be collected 10 to 15 minutes before each PE and 15 to 30 minutes after each PE procedure.

Adverse events (AEs) will be recorded before, during, and after each procedure.

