11.3. Efficacy Analysis

Efficacy Analysis will be carried out on the evaluable population. The primary efficacy analyses will also be performed using the PP population.

All efficacy variables and changes from the baseline will be summarized by visit.

For the primary efficacy variable, the ALSFRS-R Functional Scale, in addition to the overall score, values of the different functional subdomains will be summarized by visit.

For the co-primary efficacy variable, changes from baseline in the FVC will be summarized by visit.

Changes from baseline in EMG profile, ALS-CBS, ALSA-Q40, and different biomarkers (cytokine panel, neurofilament, BMAA, and immune monitoring profile) will be summarized by visit

In addition, changes from baseline in the levels of cytokine panel, neurofilament levels, and BMAA levels before and after selected PE (PE#7, PE#15, and PE#27) will be summarized and analysed using the non-parametric Wilcoxon test for paired data.

11.4. Safety Analysis.

The Safety Analysis will be based on the safety population.

All AEs (irrespective of causality) will be tabulated and summarized using descriptive statistics.

AEs will be coded in accordance with the AE classification from the MedDRA (version 17.0 or higher), and will be described by a preferred term and the system organ class for severity, causality, and seriousness.

The proportion of subjects and PE procedures temporarily associated with at least one AE/AR will be summarized.

Clinically relevant abnormal changes (according to the investigator's discretion) in vital signs and any other laboratory parameter shall be recorded as AEs. The same will be done with relevant abnormal changes in any such parameter during the follow-up period.

Clinical laboratory parameters and changes from baseline values will be summarized by visit. Vital signs and changes from baseline values will be summarized by visit.

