3.3 Determination of sample size

There has been no formal calculation for the sample size since this is a pilot study. The number of subjects planned to be included in this study is 10 subjects completing the planned treatment. The sample size is considered adequate for the evaluation of the objectives of the study. In addition, there is a rising consensus in the ALS field that active control group comparisons should be avoided in early trials (19).

Lastly, the current EMA guidance document, *Guideline on clinical investigation of medicinal products for the treatment of amyotrophic lateral sclerosis (ALS) (EMA/CHMP/4015/2013)* states that the average functional decline is about 1 point per month in untreated subjects on the ALSFRS-R Functional Scale (20). Thus, it may be assumed that 10 subjects followed during 1 year of the clinical trial would be sufficient to evaluate a change of disease progression rate. In the event that a move towards stabilization is observed, the subsequent confirmatory studies will require a formal calculation for the sample size.

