6.2 Blind review

Not applicable.

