6.4 Level of significance, multiple comparisons and multiplicity

If applicable, all statistical tests will be 2-sided and will be performed using a 5% significance level.

No adjustment for multiple comparisons or corrections for multiplicity are planned.

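### Per-protocol membership is settled with no outcome masking planned and no definition of completing treatment, so in an open-label trial of about 10 the repeated primary analysis on that set is open to outcome-dependent exclusion

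*SAP*

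**What the plan says.** SAP 5.3 sets two conditions for the PP set: the evaluable subject finished treatment, and had no major deviation capable of affecting the primary efficacy assessment. On the second condition, "The major protocol deviations will be determined in a data review meeting", and the result is recorded in a report before database lock. Neither document lists the deviations, says who attends, or says which data are shown.

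The SAP section headed "6.2 Blind review" consists of a statement that it does not apply. Protocol 3.1 and SAP 3.1 describe an open-label, single-arm study.

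On the first condition, Protocol 6.2.3 treats 27 exchanges as a maximum and accepts that "the actual number of PE sessions may be less than the maximum intended", whereas SAP 3.1 says that 27 will be carried out in total. Protocol 5.4 regards compliance measurement as not applicable. No passage gives a threshold for having finished treatment.

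Protocol 11.3 gives the PP set its role: efficacy is analysed on the evaluable population, and "The primary efficacy analyses will also be performed using the PP population". SAP 6.3.4 repeats this and includes, for the ALSFRS-R total score, a one-sample test of the observed change against a loss of 1 point per month. SAP Appendix 1 assigns the PP set six primary efficacy tables and two figures. Under SAP 6.4, "all statistical tests will be 2-sided and will be performed using a 5% significance level", and "No adjustment for multiple comparisons or corrections for multiplicity are planned".

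**The concern.** A pre-lock review protects an analysis set when something that matters is still hidden at that time, such as treatment allocation or the efficacy results. Here there is no allocation to hide, and the plan does not arrange to hide results. ALSFRS-R and FVC are collected openly at one centre over 48 weeks, so a subject's decline can be known to those who judge whether a deviation was major, or whether a subject with fewer than 27 exchanges finished treatment. Both judgements are left without a written criterion.

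With about 10 subjects, one or two exclusions can change a mean and its test noticeably. Neither document says which set prevails if the PP and evaluable results disagree. A favourable PP table could therefore be cited on its own, although its membership was decided with outcomes within reach.

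**Working it through.** **Is there a figure to reproduce?** No. SAP 3.3 says "There has been no formal calculation for the sample size since this is a pilot study", and gives no SD, effect or power. The check instead applies the SAP's own test to a trial of the planned size with no treatment effect.

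**Inputs**
- Size: n = 10. SAP 3.3 says "The number of subjects planned to be included in this study is 10 subjects completing the planned treatment". The protocol synopsis speaks of enrolling 10, so the evaluable set may be slightly larger than 10 or not.
- Test: one-sample t-test, two-sided 5%, null value a loss of 1 point per month (SAP 6.3.4, 6.4). The nominal favourable error is 2.5%.
- Truth: mean decline of exactly 1 point per month.
- Between-subject SD of the decline rate: not given in the documents. Assumed 0.5, 0.75 or 1.0 point per month where a value in points is needed.

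**Shift in the mean, normal rates.** The two most extreme of 10 standard normal values have expected sizes 1.539 and 1.001.
- Fastest decliner removed: 1.539 / 9 = 0.171 SD.
- Two fastest removed: (1.539 + 1.001) / 8 = 0.318 SD.
- For comparison, the standard error at n = 10 is 1/√10 = 0.316 SD, so two such exclusions move the mean by about one standard error.

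**Chance of a significant favourable result with no effect** (200,000 simulated trials, t-test on those remaining):

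| Excluded | Fastest decliners removed | Removed independently of outcome |
|---|---|---|
| 0 | 2.5% | 2.5% |
| 1 | 8.8% | 2.5% |
| 2 | 18.8% | 2.5% |

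**In ALSFRS-R points.** Apparent decline = 1 − SD × shift. Week 48 is 48 × 7 / 30.4375 = 11.04 months, and the difference at week 48 = SD × shift × 11.04.

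| Assumed SD | One removed: points/month | Difference at week 48 | Two removed: points/month | Difference at week 48 |
|---|---|---|---|---|
| 0.5 | 0.915 | 0.94 | 0.841 | 1.75 |
| 0.75 | 0.872 | 1.42 | 0.762 | 2.63 |
| 1.0 | 0.829 | 1.89 | 0.682 | 3.51 |

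That is 9–17% apparent slowing after one exclusion and 16–32% after two, with no true effect.

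**Sensitivity to shape.** With right-skewed (gamma) decline rates of mean 1 and SD 0.5 to 1.0, the favourable chance is 5–10% with nobody excluded, 17–29% after the fastest is removed and 34–51% after two. Part of this is not due to exclusion: the t-test already exceeds 2.5% for skewed data at n = 10.

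**The case against.** The PP analysis is a repeat. The evaluable population is named first, and SAP 5.2 asks only for one exchange plus baseline and later measurements of both ALSFRS-R and FVC, so the meeting cannot remove a fast decliner from it. The two sets of tables sit side by side. Reasons for exclusion are reported (SAP 6.3.2, Table 14.1.3), as are deviations, excluded subjects and individual scores (Listings 16.2.2, 16.2.3 and 16.2.5.1), so a reader could restore a dropped subject and recompute. The decision is documented before lock. The study is a pilot that Protocol 11.2 describes as descriptive, and confirmatory work is deferred. All of this stands. It limits the consequence, but it does not supply the missing criteria or the masking.

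Four stronger readings are tempting, and the documents do not support them:
- *That the meeting will see the outcomes.* Neither document says so. The blind-review entry is most naturally read as meaning that there is no treatment allocation to protect. What can be said is that no outcome masking is planned and that outcomes can be known.
- *That subjects who miss exchanges are the faster decliners.* Protocol 6.2.3 cites laboratory changes, clinical factors and adverse events as reasons and does not connect them with rate of decline.
- *That the whole PP package could turn into evidence of slower-than-expected decline.* Only the ALSFRS-R total is tested against an expected decline. FVC and the ALSFRS-R subdomains are tested against baseline.
- *That 9% and 19% are the error rates to expect.* They require the excluded subjects to be exactly the fastest decliners.

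One further limit is fair: masking the meeting does nothing about subjects who stop early and so leave the PP set without any judgement being made.

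**Conclusion.** The point holds for the PP results only. Their membership rests on deviations that are not listed in advance, on an undefined notion of finished treatment, and on a meeting for which no outcome masking is planned. Outcome-dependent exclusion is therefore possible; the documents do not show that it is intended or likely.

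For normal rates and 10 evaluable subjects, the ceiling is a rise in favourable error from 2.5% to about 9% (one exclusion) or 19% (two) in the single ALSFRS-R test against 1 point per month. The percentages for normal rates do not depend on the assumed SD, but the figures in points do. Skewed rates would give larger values. If exclusion is independent of outcome, there is no inflation. The evaluable analysis is untouched. This is a cheap improvement worth making, not a defect in the lead analysis.

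**What to change.** 1. **SAP 6.2.** Replace the present entry with a rule that PP membership is classified and signed off from a deviation and exposure listing from which all post-baseline ALSFRS-R and FVC values have been removed, before any efficacy output is run.
2. **SAP 5.3.** State in advance which categories of deviation exclude a subject, and what exposure counts as completing treatment for the purpose of this analysis set. The sponsor should choose the definition and, in doing so, reconcile Protocol 6.2.3 (27 as a maximum, fewer allowed) with SAP 3.1 (27 to be conducted).
3. **SAP 6.3.4.** State that the PP results support the evaluable analysis and cannot carry an efficacy statement alone. This also covers early stoppers, whom masking does not address.

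The cost is a few sentences and one listing with the efficacy columns suppressed. The numbers of exchanges are already summarised (SAP 6.3.6) and deviations already listed (Listing 16.2.2), so no new data are needed. The downside is slightly less freedom to judge unforeseen deviations.

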5.4 Safety Population

All subjects who receive any amount of the study drug.

6 STATISTICAL AND ANALYTICAL PLANS

The tables and listings planned for the analysis are detailed in Appendix I.

6.1 Changes in the planned analyses

Any changes in the statistical analyses once the SAP has been finalised and after locking the database should be documented and justified on a file note and the clinical study report.

6.2 Blind review

Not applicable.

6.3 Hypotheses and statistical methods

6.3.1 Summary statistics

Data will be presented using summary statistics.

All categorical variables will be summarized in frequency and percentage.

The continuous variables will be reported by sample statistics: n (number of observations), number of missing data, mean, standard deviation (SD), minimum, first quartile (Q1), median, third quartile (Q3), and maximum. The 95% Confidence Interval for the mean will be added for the primary and secondary efficacy variables, as well as p-value for test comparisons when necessary (see sections 6.3.4 and 6.3.5 for details).

The number of digits behind the decimal point will be 1 in tables with percentages.

The summary statistics minimum and maximum will be presented to the same number of decimal places as that used to collect the data, while mean, median, Q1 and Q3 will be presented to one more decimal places, and standard deviation will be presented to two more decimal places.

All the analysis will be performed using SAS® Enterprise Guide system version 7.11.

6.3.2 Disposition of subjects

Subject disposition including the number of subjects enrolled in the study, number of subjects prematurely withdrawn from the study and the reasons of withdrawal will be presented.

The number of subjects included in the study, number of subjects included in evaluable, per protocol, and in safety populations, according to the definitions described in section 5, will be described, as well as the reasons from exclusion from each one of these populations.

Number of patients who fulfill or not the inclusion and the exclusion criteria will be presented, for each criteria described in section 3.2.

6.3.3 Demographic and other baseline characteristics

The following demographic and baseline data will be described at Baseline visit (V0):

- Age (see definition part 6.3.10), gender, race, ethnicity, height, weight
- ALS medical history: time since diagnosis, body part first affected by the disease, current status findings, and revised El Escorial-Arlie Criteria
- Relevant medical and surgical history (presented in alphabetical order)
- Pregnancy test (performed yes/no, and result)
- Past assessment of primary endpoints: ALSFRS-R score and FVC score values before baseline visit, i.e. from the last 6 months prior to enrolment
- Peripheral venous access assessment

6.3.4 Primary efficacy analysis

The primary efficacy analyses will be carried out on the evaluable population, and will also be performed using the PP population.

For the primary efficacy variable, the ALSFRS-R Functional Scale, in addition to the overall score, values of the different individual questions, and functional subdomains will be summarized by visit.

For all these variables, and for the co-primary efficacy variable, FVC, changes from baseline will be summarized by visit.

Differences between baseline and subsequent visits for the ALSFRS-R overall and for the bulbar, fine/gross motor and respiratory subdomains will be analysed using the student t-test (normal distribution) or nonparametric Wilcoxon signed-rank test. Comparison between ALSFRS-R Overall change from baseline values obtained versus expected ALSFRS-R Overall change from baseline values according to EMA guideline, i.e. decrease of 1 point by month, will be analysed using the one-sample student t-test in the cases where the assumptions of normality are met, or nonparametric Wilcoxon signed-rank test if not.

Differences between baseline and subsequent visits for the Forced Vital Capacity (FVC), in liters and percentage will be analysed using the student t-test (normal distribution) or nonparametric Wilcoxon signed-rank test.

ALS Functional Rating Scale – Revised (ALSFRS-R):

This test is a validated rating instrument for progression of disability in ALS that provides an estimate of the degree of the subject's functional impairment through a short questionnaire. The ALSFRS-R includes 12 questions to assess the level of self-sufficiency of subjects in various functional domains. Aspects of nourishment, personal care, personal autonomy, and communication are also evaluated. Each task is graded on a five point scale from 0 (not able to do) to 4 (normal ability). Individual scores are totaled to produce a final result of between 0 (worst) and 48 (best).

ALSFRS-R will be classified as following, between 3 subdomains:

- Bulbar function (questions #1 to #3),
- Fine and gross motor function (questions #4 to #9),
- Respiratory function (questions #10 to #12).

Note: item #5 (cutting food) is divided into 2 sub-items: #5a (without gastrostomy) and #5b (with gastrostomy). Only one of them can be filled, and the other one should be missing.

In case of any item is missing, the total score and the corresponding subdomain score will be considered missing.

Pulmonary Function: Forced Vital Capacity (FVC):

The FVC measures the volume of air that a person can forcibly exhale through a spirometer after a full inspiration. Following the recommendations of the American Thoracic Society and European Respiratory Society this should be measured in a seated position, which facilitates subjects to be able perform multiple measurements if necessary. The result obtained is expressed in a percentage over the expected result in the general population.

6.3.5 Secondary efficacy analyses

Changes from baseline in EMG profile (sensory NCS and motor NCS), ALS-CBS, ALSA-Q40, and different biomarkers such as cytokine panel (plasma/CSF), neurofilament (plasma/CSF), BMAA (plasma/CSF), and immune population profile (plasma) will be summarized by visit.

In addition, changes in the EMG profile, ALS-CBS, ALSA-Q40, plasma cytokine panel, plasma neurofilament levels, and plasma BMAA levels before and after selected PE (PE#7, PE#15, and PE#27) will be summarized and analyzed using the non-parametric Wilcoxon signed-rank test for paired data.

ALS Cognitive Behavioral Screen (ALS-CBS):

This test is designed as a screening tool to help identify subjects at risk for frontotemporal cognitive impairment and/or behavioral disorders. As such, this tool should not be used to establish a diagnosis, and a clinical neurological assessment will be required for diagnosis of ALS on all subjects prior to the test.

The test is composed by two sections. The first section is a 4 subdomain cognitive screening consisting of: Attention (complex orders, mental sums, language, and eye movement); Concentration (inversion of numeric series); Follow-up and monitoring (reverse sequences, alphabet, number and letter sequencing); and Initiation and Recovery (nomination). The second section consists of a questionnaire with 15 items of behavioral changes assessed by the caretaker.

The result of the cognitive section is a score of 0 to 20, based on the accuracy of the responses and the errors committed. The result of the behavioral section is the sum of the items on a Likert Scale.

A cognitive screening score will be computed, as the sum of the 4 items of the cognitive section (test 2): attention, concentration, tracking and monitoring, initial and retrieval.

In case of any item is missing, the cognitive score will be considered missing.

ALS Assessment Questionnaire 40 (ALSA-40):

This specific ALS quality of life questionnaire provides insight on situations of great importance for ALS subjects in areas such as mobility, fear of falling when walking, difficulty eating and cutting, participation in meetings, feelings of isolation, embarrassing social situations, feelings of fear and hopelessness in the future, and problems associated with motor neuron disease.

The questionnaire consists of 40 items grouped into 5 representative dimensions associated with quality of life:

- Physical mobility (questions #1 to #10),
- Activities of daily living (questions #11 to #20),
- Food and drink (questions #21 to #23),
- Communication (questions #24 to #30),
- Emotional function (questions #31 to #40).

Each question is scored from 0 to 4 according to a gradation of symptom onset frequency (never, rarely, sometimes, often, and always). From raw scores, an index from 0 to 100 is obtained for each dimension, which make comparisons with the other dimensions possible as well as a straightforward interpretation of the results (0 = better state of health as measured by the questionnaire; 100 = poorer state of health). The first 4 scales refer to deficits and subsequent disabilities as a result of the disease. The fifth scale reflects how the subject is facing his/her physical deterioration emotionally.

Data for ALSA-40 will be presented using raw scores (original values, i.e. physical mobility ranging from 0 to 40, food and drink ranging from 0 to 12), and using transformed scores (all the 5 dimensions scores ranging from 0 to 100).

Electromyography (EMG)

Surface EMG will be performed to record motor evoked potential in the distal muscles of the upper limbs (thenar and hypothenar eminence) and dorsiflexor muscles of the lower limbs (anterior tibialis) after electrical stimulation on the median, ulnar, and external popliteal sciatic nerve. Sensory nerve conduction studies (NCS), Motor NCS will be listed.

CSF and plasma samples

Values and change from baseline values will be summarized by visit. The following parameters will be evaluated:

- CSF standard analysis (see in "Other safety assessments", section 6.3.9)
- Plasma cytokine panel
- CSF cytokine panel
- Plasma neurofilament analysis
- CSF neurofilament analysis

- Plasma BMAA levels
- CSF BMAA levels
- Plasma immune population profile

